6.4 Treatment blinding

Subjects, investigator staff, persons performing the assessments, and Clinical Trial Team (CTT) will remain masked to the identity of the treatment from the time of randomization until database lock, using the following methods: (1) Randomization data are kept strictly confidential until the time of unblinding and will not be accessible by anyone involved in the study. (2) the identity of the treatments will be concealed by the use of study treatment that are all identical in packaging, labeling, schedule of administration, appearance, taste, and odor.

Unmasking of the CTT members/site staff will occur at the end of Part 1 and again at the end of Part 2.

Role	Time and Event		
	Randomization list generated	Treatment allocation & dosing	Safety event (single subject unblinded)
Subjects/Patients	В	В	В
Site staff	В	В	В
Drug Supply and Randomization Office	UI	UI	UI
Bioanalytical Team	UI	UI	UI
Statistician/statistical programmer/data analysts	В	В	В
All other sponsor staff not identified above	В	В	В
B Remains blinded			
UI Allowed to be unblinded on individ	lual patient level		

6.5 Dose escalation and dose modification

Investigational or other study treatment dose adjustments and/or interruptions are not permitted.

6.5.1 Dose modifications

Dose interruptions and/or reductions are not allowed.

6.5.2 Follow-up for toxicities

Not applicable

6.6 Additional treatment guidance

6.6.1 Treatment compliance

The Investigator must promote compliance by instructing the subject to dose the study treatment exactly as prescribed and by stating that compliance is necessary for the subject's safety and the validity of the study. The subject must also be instructed to contact the Investigator if he/she is unable for any reason to dose the study treatment as prescribed.

Compliance will be assessed by the Investigator and/or study personnel at each visit by questioning the subject and verifying drug accountability including the number of used and unused BFS containers. This information should be captured in the source document at each visit.

All study treatment dispensed and returned must be recorded in the Drug Accountability Log.

6.6.2 Recommended treatment of adverse events

At present, there is insufficient information to provide specific recommendations regarding treatment of adverse events (AEs). Due to the expected lack of systemic exposure of the drug, the nature of ECF843 as an endogenous protein, and the fact that to date there have been no significant adverse events (ocular or non-ocular), an abundance of caution is not warranted at this time point.

If the subject were to experience significant discomfort upon instillation of the investigational product, the eye should be flushed with sterile saline (or equivalent). Should the subject experience blurred vision for a time just after instillation of the investigational product, he/she should not drive or use machines until the effect has worn off. The Investigator must treat the subject as needed and appropriate for their condition.

Medication used to treat AEs must be recorded on the appropriate eCRF.

6.6.3 Emergency breaking of assigned treatment code

Emergency code breaks must only be undertaken when it is required to in order to treat the subject safely. Blinding codes may also be broken after a subject discontinues treatment due to disease progression if deemed essential to allow the investigator to select the subject's next treatment regimen, and after discussion and agreement with the sponsor. Most often, study treatment discontinuation and knowledge of the possible treatment assignments are sufficient to treat a study subject who presents with an emergency condition. Emergency treatment code breaks are performed using the IRT. When the investigator contacts the system to break a treatment code for a subject, he/she must provide the requested subject identifying information and confirm the necessity to break the treatment code for the subject. The investigator will then receive details of the investigational drug treatment for the specified subject and a fax or email confirming this information. The system will automatically inform the Novartis/sponsor monitor for the site and the study team that the code has been broken.

It is the investigator's responsibility to ensure that there is a dependable procedure in place to allow access to the IRT at any time in case of emergency. The investigator will provide:

- protocol number
- subject name (if available)
- subject number

In addition, oral and written information to the subject must be provided on how to contact his/her backup in cases of emergency, or when he/she is unavailable, to ensure that un-blinding can be performed at any time.

Subjects will be discontinued from the study once the treatment code has been broken.

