REML	residual/restricted maximum likelihood
RNA	ribonucleic acid
SAE	serious adverse event
SANDE	Symptom Assessment in Dry Eye
SAP	statistical analysis plan
SMQ	standardized MedDRA query
SUSAR	suspected unexpected serious adverse reactions
TBUT	tear breakup time
TFOS DEWS II	Tear Film and Ocular Surface Society Dry Eye Workshop II
TID	ter in die (three times daily)
TNF	tumor necrosis factor
UI	International Unit
US	United States
WHO	World Health Organization

Assessment	A procedure used to generate data required by the study
Clinical Outcome Assessment (COA)	A measure that describes or reflects how a subject feels, functions, or survives
Cohort	A specific group of subjects fulfilling certain criteria
Control drug	A study drug used as a comparator to reduce assessment bias, preserve blinding of investigational drug, assess internal study validity, and/or evaluate comparative effects of the investigational drug.
Discontinuation from study	Point/time when the subject permanently stops receiving the study treatment and further protocol required assessments or follow-up, for any reason. No specific request is made to stop the use of their samples or data.
Discontinuation from study treatment	Point/time when the subject permanently stops receiving the study treatment for any reason (prior to the planned completion of study drug administration, if any). Subject agrees to the other protocol required assessments including follow-up. No specific request is made to stop the use of their samples or data.
Dosage	Dose of the study treatment given to the subject in a time unit (e.g. 100 mg once a day, 75 mg twice a day)
Enrollment	Point/time of subject entry into the study at which informed consent must be obtained (i.e. prior to starting any of the procedures described in the protocol). The action of enrolling one or more subjects.
Estimand	As defined in the ICH E9(R1) addendum, estimand is a precise description of the treatment effect reflecting the clinical question posed by the trial objective. It summarizes at a population-level what the outcomes would be in the same subjects under different treatment conditions being compared. Attributes of an estimand include the population, variable (or endpoint) and treatment of interest, as well as the specification of how the remaining intercurrent events are addressed and a population level summary for the variable.

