9.1 Discontinuation

9.1.1 Discontinuation of study treatment

Discontinuation of study treatment for a subject occurs when study treatment is permanently stopped for any reason (prior to the planned completion of study drug administration, if any) and can be initiated by either the subjector the investigator

Discontinuation from study treatment is required under the following circumstances:

- Subject/guardian decision
- Pregnancy
- Use of prohibited treatment as per recommendations in the prohibited treatment section (see Section 6.2.2)
- Any situation in which continued study participation might result in a safety risk to the subject
- Inability or unwillingness of the subject to follow the protocol requirements
- Following emergency unblinding (see Section 6.6.3)
- Adverse events that indicate a safety risk to the subject
- Unsatisfactory therapeutic effect

If discontinuation from study treatment occurs, the investigator should make a reasonable effort to understand the primary reason for the subject's premature discontinuation of study treatment and record this information.

Subjects who discontinue from study treatment agree to return for the end of treatment and follow-up visits indicated in the Assessment Schedule (refer to Section 8).

If the subject cannot or is unwilling to attend any visit(s), the site staff should maintain regular telephone contact with the subject, or with a person pre-designated by the subject. This telephone contact should preferably be done according to the study visit schedule.

After study treatment discontinuation, at a minimum, in abbreviated visits, the following data should be collected at clinic visits or via telephone/email contact:

- New / concomitant treatments
- Adverse Events / Serious Adverse Events

The investigator must also contact the IRT to register the subject's discontinuation from study treatment.

If discontinuation occurs because treatment code has been broken, please refer to Emergency breaking of treatment code section.

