9.1.2 Discontinuation from study

Discontinuation from study is when the subjectpermanently stops receiving the study treatment, and further protocol-required assessments or follow-up, for any reason. If the subject agrees, a final evaluation at the time of the subject's study discontinuation should be made as detailed in the assessment table (refer to Section 8).

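### Protocol 6.6.3 takes subjects out of the study after any code break, against the treatment-only discontinuation in 9.1.1, and so shortens safety follow-up for the few subjects unblinded for safety

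*Protocol*

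**What the plan says.** Protocol 6.6.3 allows an emergency code break only where it is needed to treat the subject safely. It adds a second case: "Blinding codes may also be broken after a subject discontinues treatment due to disease progression", subject to sponsor agreement. It closes with a rule covering both: "Subjects will be discontinued from the study once the treatment code has been broken".

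Protocol 9.1.1 lists the circumstances that require stopping study treatment, and one of them is "Following emergency unblinding (see Section 6.6.3". It then sets the follow-up: "Subjects who discontinue from study treatment agree to return for the end of treatment and follow-up visits indicated in the Assessment Schedule". A floor is added: "After study treatment discontinuation, at a minimum, in abbreviated visits, the following data should be collected at clinic visits or via telephone/email contact". The data named are new or concomitant treatments and AEs/SAEs. The section ends: "If discontinuation occurs because treatment code has been broken, please refer to Emergency breaking of treatment code section".

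The glossary treats leaving treatment and leaving the study as different statuses. A subject who discontinues from the study "permanently stops receiving the study treatment and further protocol required assessments or follow-up, for any reason". Section 9.1.2 says the same, ending "further protocol-required assessments or follow-up, for any reason". A subject who discontinues treatment only goes on with assessments and follow-up.

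**The concern.** One event is given two statuses with different follow-up. An emergency break happens because the subject's safety calls for it, so these are subjects whose later safety data are wanted. If 6.6.3 is applied as written, the subject has one early final visit, and the follow-up that 9.1.1 already provides does not take place. At stake is the completeness of individual safety follow-up for a product on which Protocol 4.5 describes clinical experience as limited.

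**Working it through.** The plan states no figure to reproduce. The check compares the texts, then counts scheduled days.

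**Which rule governs.** Section 9.1.1 points to 6.6.3 twice, in the list entry and in its closing sentence. Leaving the study includes stopping treatment, so the list entry is not false under 6.6.3. The natural reading is that 6.6.3 decides. However, 9.1.1 never says that its own follow-up rule is set aside. Its closing reference is also limited to discontinuation caused by the code break. It does not fit a break made after treatment had already stopped for disease progression, where 9.1.1 follow-up would be under way and 6.6.3 would end it.

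**What follow-up 6.6.3 leaves.** Inputs:
- Section 8: a prompt final visit with the final-visit assessments after study discontinuation.
- Section 10.1.1: AE collection through the end-of-study visit; AEs already detected are followed to resolution or until judged permanent.
- Section 10.1.3: SAEs of any cause reported for 30 days past the last study visit; after that, only those suspected to be related to treatment.
- Table 8-1: Part 1 ends on Day 56. Table 8-2: Part 2 treatment ends on Day 84.

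Assume that the break and the final visit both fall on Day d, that the final visit counts as end of study, and that under 9.1.1 the subject would have attended to the end of the part.

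Part 1: AE days lost = 56 − d. The SAE window closes on d + 30, against 56 + 30 = Day 86.

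| Assumed d | New non-serious AE days lost | SAE window closes (6.6.3) | SAE window closes (9.1.1, at most) |
|---|---|---|---|
| 14 | 56 − 14 = 42 | Day 44 | Day 86 |
| 28 | 56 − 28 = 28 | Day 58 | Day 86 |
| 42 | 56 − 42 = 14 | Day 72 | Day 86 |

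Part 2, d = 14, counted only to Day 84: the window closes on 14 + 30 = Day 44, against 84 + 30 = Day 114. Later visits are left out because their footnote is not legible in the copy reviewed.

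**Trial level.** The documents give no code-break rate. With an assumed 0.1% to 1% of the roughly 680 Part 1 subjects (Protocol 5), 0.001 × 680 = 0.68 to 0.01 × 680 = 6.8 subjects are affected. If every break fell on Day 14, the loss would be 0.68 × 42 = 28.6 to 6.8 × 42 = 285.6 subject-days. Out of 680 × 56 = 38,080, that is 0.075% to 0.75%.

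**Analyses.** Protocol 12.4.3 and SAP Table 2-4 treat data after treatment discontinuation as missing in the primary analysis, so continued follow-up would not change it. Protocol 12.4.6 and SAP Table 2-5 use such data in the supplementary analysis.

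**The case against.** The strongest reply is that the plan already has a routing rule: the general section sends this case to the specific one, and the specific one says the subject leaves the study. That largely stands. A reader might infer that sites are free to follow either rule; the two references to 6.6.3 make that an overstatement. But if 6.6.3 governs, shorter follow-up is simply the rule.

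Second, most of the important safety data survive. The event that prompts an emergency break will normally be a detected AE and is followed to its outcome. This stands, and it limits the loss to new non-serious AEs after the final visit and to later SAEs not suspected to be related. It would be wrong to infer that safety follow-up stops altogether.

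Third, the days lost are upper bounds. Section 9.1.1 accepts telephone or email contact when a subject will not attend, and the SAE window runs from the last study visit, so Day 86 is not assured under 9.1.1 either. This stands.

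Fourth, a break after disease progression serves to choose the next treatment and is not a safety emergency. This also stands: that case shows the texts do not fit together, but the safety argument rests on emergency breaks.

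Fifth, keeping unmasked subjects lets unmasked values into the supplementary analysis. This is true. It is a small cost of the fix.

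**Conclusion.** The conflict is real, and its likely effect is shortened safety follow-up for a few subjects. For a Day 14 break in Part 1, up to 42 days of new non-serious AE collection are lost, and the all-cause SAE window closes on Day 44 instead of at most Day 86. These figures rest on an assumed break day, a final visit on that day, and full attendance under 9.1.1. The number of subjects rests on an assumed rate.

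A reader might go on to infer biased results or lost efficacy data. The documents do not support this: the primary analysis drops these data anyway, and the 9.1.1 minimum contact requires neither SANDE nor staining. Table 6-3 also codes site staff as staying masked at a single-subject safety unblinding, although 6.6.3 gives the investigator the treatment. That mismatch has no consequence of its own and is editorial at most.

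The point is small, but worth correcting because the follow-up it would restore already exists in the protocol.

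**What to change.** Replace the last sentence of 6.6.3 with wording such as: *A code break ends study treatment only; safety follow-up and the recording of AEs, SAEs and concomitant treatments go on as in 9.1.1, provided the subject agrees.* The reference from 9.1.1 to 6.6.3 then leads to a consistent rule.

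In the SAP, state that SANDE or staining values collected after the break stay in the treatment-policy supplementary analysis and are identified in a listing as post-unmasking. The listing is useful because the investigator grades staining (Protocol 8.3.3) and receives the treatment details at a code break (6.6.3).

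The cost is one protocol sentence and one SAP statement with its listing, with no new procedure. The downside is that a few unmasked values may enter the supplementary analysis. No change to Table 6-3 is needed beyond an optional editorial one.

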6.7 Preparation and dispensation

Each study site will be supplied with study drug in packaging as described under investigational and control drugs section.

A unique medication number is printed on the study medication label.

For both Part 1 and Part 2, Investigator staff will identify the study medication kits to dispense to the subject by contacting the IRT and obtaining the medication number(s). The study medication secondary packaging has a 2-part label (base plus tear-off label). Immediately before dispensing the medication kit to the subject, site personnel will detach the outer part of the label from the packaging and affix it to the source document.

As per Section 4.6 during a Public Health emergency as declared by Local or Regional authorities i.e. pandemic, epidemic or natural disaster, that limits or prevents on-site study visits, delivery of IMP directly to a subject's home may be permitted (if allowed by Local or Regional

Health Authorities and IRBs/IECs as appropriate) in the event the Investigator has decided that an on-site visit by the subject is no longer appropriate or possible, and that it is in the interest of the subject's health to administer the study treatment even without performing an on-site visit. The dispatch of IMP from the site to the subject's home remains under the accountability of the Investigator. Each shipment/provisioning will be for a maximum of 2 week supply. In this case, regular phone calls or virtual contacts (e.g., every 2 weeks or more frequently if needed) will occur between the site and the subject for instructional purposes, safety monitoring, investigation of any adverse events, ensuring subjects continue to benefit from treatment, and discussion of the subject's health status until the subjects can resume visits at the study site.

6.7.1 Handling of study treatment and additional treatment

6.7.2 Handling of study treatment

Study treatment must be received by a designated person at the study site, handled and stored safely and properly and kept in a secured location to which only the investigator and designated site personnel have access. Upon receipt, all study treatment must be stored according to the instructions specified on the labels and in the Investigator's Brochure. Clinical supplies are to be dispensed only in accordance with the protocol. Technical complaints are to be reported to the respective Novartis CO Quality Assurance.

Medication labels will be in the local language and comply with the legal requirements of each country. They will include storage conditions for the study treatment but no information about the subject except for the medication number.

The investigator must maintain an accurate record of the shipment and dispensing of study treatment in a drug accountability log. Monitoring of drug accountability will be performed by monitors during site visits or remotely and at the completion of the trial. Subjects will be asked to return all used and unused study treatment and packaging at the end of the study or at the time of discontinuation of study treatment.

At the conclusion of the study, and as appropriate during the course of the study, the investigator will return all used and unused study treatment, packaging, drug labels, and a copy of the completed drug accountability log to the Novartis monitor or to the Novartis address provided in the investigator folder at each site.

6.7.3 Handling of additional treatment

Not applicable

6.7.4 Instruction for prescribing and taking study treatment

Table 6-4Dose and treatment schedule

Investigational / Control Drug	Dose	Frequency and/or Regimen
ECF843 0.15 mg/mL	one drop in each eye	BID
ECF843 0.15 mg/mL	one drop in each eye	TID
ECF843 0.45 mg/mL	one drop in each eye	TID
Vehicle	one drop in each eye	BID or TID as per study design

Part 1

Each single use BFS container contains enough drug for instillation of one drop per eye at each dosing time point. There will be additional drug remaining in the container after dosing. However, subjects must NOT continue dosing beyond the single time point with any container.

Drug must be stored as indicated on the container label.

Subjects will dose according to their randomized dosing frequency (BID or TID). If dosing BID, subjects will dose in the morning upon wakening and in the evening prior to bed time. If dosing TID, subjects will dose morning upon wakening, mid-day, and evening prior to bed time. Subjects should avoid touching the tip of the container to any surface, including the eye or surrounding skin, to avoid contamination.

Part 2

ECF843 and Vehicle will be handled as described above; the dose frequency will be derived from the Part 1 results.

All kits of study treatment assigned by the IRT will be recorded in the IRT system.

7 Informed consent procedures

Eligible subjects may only be included in the study after providing (witnessed, where required by law or regulation) Institutional Review Board/Independent Ethics Committee (IRB/IEC)-approved informed consent.

If applicable, in cases where the subject's representative(s) gives consent (if allowed according to local requirements), the subject must be informed about the study to the extent possible given his/her understanding. If the subject is capable of doing so, he/she must indicate agreement by personally signing and dating the written ICF.

Informed consent must be obtained before conducting any study-specific procedures (e.g. all of the procedures described in the protocol). For this study, the subject must sign informed consent prior to participation in Part 1, and again confirm and sign the informed consent prior to participation in Part 2 (the main informed consent form for a single subject contains both signatures). In the case of subjects who are enrolled only in Part 2, only 1 signature is required. The process of obtaining informed consent must be documented in the subject source documents.

Novartis will provide to investigators in a separate document a proposed ICF that complies with the International Council for Harmonisation Good Clinical Practice (ICH GCP) guidelines and regulatory requirements and is considered appropriate for this study. Any changes to the proposed consent form suggested by the investigator must be agreed by Novartis before submission to the IRB/IEC.

[figure not shown]
Information about common side effects already known about the investigational drug can be found in the Investigator's Brochure (IB). This information will be included in the subject informed consent and should be discussed with the subject during the study as needed. Any new information regarding the safety profile of the investigational drug that is identified between IB updates will be communicated as appropriate, for example, via an investigator notification or

an aggregate safety finding. New information might require an update to the informed consent and then must be discussed with the subject.

The following informed consents are included in this study:

- Main study informed consent, which also includes:
 - A subsection that requires a separate signature for the 'Optional Consent for Additional Research' to allow future research on data/samples collected during this study
 - As applicable, Pregnancy Outcomes Reporting Consent for female subjects or the female partners of any male subjects who took study treatment

Women of child bearing potential must be informed that taking the study treatment may involve unknown risks to the fetus if pregnancy were to occur during the study and agree that in order to participate in the study, they must adhere to the contraception requirements.

A copy of the approved version of all consent forms must be provided to Novartis after IRB/IEC approval.

8 Visit schedule and assessments

Assessment schedules (Table 8-1 and Table 8-2) list when all of the assessments are to be performed. All data obtained from these assessments must be supported in the subject's source documentation.

Only subjects assigned exclusively to vehicle treatment in Part 1 may be eligible to participate in Part 2 of the study. A list of subjects eligible for screening in Part 2 of the study will be discussed between the Investigator and the Sponsor prior to initiating screening visits. In the event a study site was initiated close to the end of enrollment and did not have sufficient time to begin recruiting subjects in Part 1, the site may enroll subjects into Part 2 of the study if approved by the Sponsor.

Subjects are encouraged to stick to the scheduled visits as much as possible. If a subject is unable to return to the site as per the visit schedule, no visits should be missed, and efforts should be made to resupply the subject with sufficient drug (as needed). Subjects should be seen for all visits/assessments as outlined in the assessment schedule (Table 8-1 and Table 8-2) as close as possible to the target visit day and as close to the same time of day for each visit as possible. If a subject returns to the site for a visit earlier or later than planned, the next sequential visit should take place. The remaining subsequent visits should then be scheduled in a way that

brings the subject back to their original target dates for each visit as determined at Screening/Baseline.

Subjects must not have dosed with study medication within 4 hours of the visit assessments being conducted.

Missed or rescheduled visits should not lead to automatic discontinuation.

Subjects who prematurely discontinue the study for any reason should be scheduled for a visit as soon as possible, at which time all of the assessments listed for the final visit will be performed. At this final visit, all dispensed investigational product must be reconciled, and the adverse event and concomitant medications recorded on the eCRF.

Period Treatment Screening Visit Name Visit 1-Screening Visit 2 Visit 3 Visit 4 Visit 5/EOS Visit 1-Randomization 28 Days 1 14 42 56 1 Informed consent Х Х Inclusion / Exclusion criteria Demography Х Medical history/current medical conditions X Concomitant medications Х Х Х Х Х Pregnancy Test (urine) Х Х Х In office SANDE score Х Corrected visual acuity Х Х Х Х х Х Х х Х Slit lamp biomicroscopy Х Ocular hyperemia Х Х Х Х Tear break-up time (TBUT) Х Х Х Х Х х Corneal fluorescein staining² Х Х Х Х Х Х Х Х Х Conjunctival lissamine staining Schirmer Tear Test Х Intraocular Pressure (IOP) Х Х Х Х Х Fundus Exam Х Х Contact IRT³ Х Х Х Х Randomization Х Dispense study medication Х Х Х Х Х In-office study drug administration

Table 8-1 **Assessment Schedule, Part 1**

Novartis	Confidential	
Amended Protocol Version 01 (Clean)		Pro

Page 39 Protocol No. CECF843A2201

Period	Screening	Treatment						
Visit Name	Visit 1-Screening	Visit 1-Randomization	Visit 2	Visit 3	Visit 4	Visit 5/EOS		
Days	1	1	14	28	42	56		
Adverse Events	Х	x	Х	Х	Х	Х		
At home SANDE questionnaire (eDiary) ⁴	Х		Х	Х	Х			
Study completion information						Х		
X Assessment to be recorded in the clinica	l database or received e	ectronically from a vendor			•	÷		

3 Sites will enter average SANDE score (obtained from the electronic diary) and the corneal fluorescein staining score from the eye with the highest composite score (sum of the 5 regions)

4 Subjects will complete an electronic diary once daily (in the evening before bed time and prior to the evening dose of study medication) from Visit 1-Screening through to the end of the study (at home SANDE questionnaire)

Table 8-2Assessment Schedule, Part 2

Period	Screening	Treatment	eatment						Post Treatment Follow-up		
Visit Name	Visit 1	Visit 2	Visit 3	Visit 4	Visit 5	Visit 6	Visit 7/ EOT	Visit 8/ EOS ⁸	Safety F/U EOS ⁸ +4. +8, +12 Weeks		
Days	-14	1	7	14	28	42	84	126	154, 182, 210		
Informed consent	х										
Inclusion / Exclusion criteria	x	x									
Demography	Х										
Medical history/current medical conditions	x										
Concomitant medications	x	x	x	x	x	x	x	x	x		
Pregnancy Test (urine)	Х						X				

Period	Screening	Treatment						Post Treat	tment Follow-up
Visit Name	Visit 1	Visit 2	Visit 3	Visit 4	Visit 5	Visit 6	Visit 7/	Visit 8/ EOS ⁸	Safety F/U EOS ⁸ +4. +8, +12 Weeks
Days	-14	1	7	14	28	42	EOT 84	126	154, 182, 210
In office SANDE score	X	X		14	20	72	04	120	134, 102, 210
Corrected visual acuity		Х					Х		
				.					
Slit lamp biomicroscopy	х	Х	Х	х	х	Х	Х		
Ocular hyperemia		х	Х	х	х	Х	Х		
	1								
Tear break-up time	x	x			х		x		
(TBUT)									
Corneal fluorescein staining ³	х	х	х	х	х	x	х		
staining									
Conjunctival lissamine									
staining	Х	х	Х	Х	Х	Х	Х		
Schirmer Tear Test	Х	x							
Intraocular Pressure				-					

Novartis Amended Protocol Version 01 (Clean)

Page 40 Protocol No. CECF843A2201

Confidential

Period	Screening	Treatment						Post Trea	tment Follow-up
Visit Name	Visit 1	Visit 2	Visit 3	Visit 4	Visit 5	Visit 6	Visit 7/ EOT	Visit 8/ EOS ⁸	Safety F/U EOS ⁸ +4. +8, +12 Weeks
Days	-14	1	7	14	28	42	84	126	154, 182, 210
Fundus exam		Х					Х		
Randomization		Х							
Dispense study drug	Х	Х		Х	Х	Х			
In-office study drug administration		х		х	x	x			
Adverse Events ⁶	х	Х	Х	Х	Х	Х	Х	Х	Х
At home SANDE questionnaire (eDiary) ⁷	x	x	x	x	x	x			
Study completion							x		
X Assessment to be reco	orded in the clir	nical database	or received ele	ctronically from	n a vendor				

Novartis Amended Protocol Version 01 (Clean)

Confidential

Page 41 Protocol No. CECF843A2201

Period	Screening	Treatment		Post Treatment Follow-up					
Visit Name	Visit 1	Visit 2	Visit 3	Visit 4	Visit 5	Visit 6	Visit 7/ EOT	Visit 8/ EOS ⁸	Safety F/U EOS ⁸ +4. +8, +12 Weeks
Days	-14	1	7	14	28	42	84	126	154, 182, 210
	plete an electronic d isit 1 (Screening) th				aily (in the eve	ning before be	d time and pric	r to the evenin	ng dose of study

Novartis Amended Protocol Version 01 (Clean)

Page 42 Protocol No. CECF843A2201

Confidential

